Picterus AS is a private limited liability company founded in Trondheim, Norway. They have developed a new smartphone app, Picterus Jaundice Pro (Picterus JP), that combines previous research on the bio-optics of jaundice in newborn skin with a mHealth approach.  Picterus JP uses an algorithm based on color analysis of a digital image to estimate the bilirubin levels in the blood, together with a unique color calibration card to adjust for different light conditions and the automatic adjustments in the phone (figure 2).

[figure not shown]

Fig. 2 Workflow of Picterus JP system. A) A photo of the newborn is taken, B) colors from the calibration card are used to calibrate the image, C) calibrated colors are compared with an extensive database of color- and bilirubin pairs, and D) the matching bilirubin estimate is presented to the user.

Picterus JP has been tested in 350 Caucasian and 170 Latin-American newborns, with mainly parents' skin types 1 to 4 according to the Fitzpatrick scale (Figure 3) and skin color 1 to 3 according to Neomar's neonatal skin color scale (Figure 4).  $^{20,21}$  The studies showed a Pearson correlation index of 0.83 to 0.88 and sensitivity of 90 to 100% to detect newborns with severe jaundice, defined as TSB above 250 µmol/L and specificity of 70 to 80%.

However, there is still uncertainty about how Picterus JP works in newborns with high melanin content (Asian and African population / Neomar's scale 4). Melanin could potentially influence the results, as it is one of the essential absorbers of light in the skin. However, melanocytes are immature at birth, and melanin levels in the skin are lower in newborns compared to adults.

Fig. 3 Fitzpatrick scale

Fig. 4 Neomar's skin color scale for newborns 

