#### 1.2. Problem statement

Picterus performed a pilot study in Uganda from December 2019 to March 2020, which included 167 newborns. Results showed a Pearson correlation index of 0.59 between TSB and the Picterus image estimate, a sensitivity of 66%, and a specificity of 94%, when the cut-off was set to 250  $\mu$ mol/L. Only six newborns had bilirubin levels higher than 250  $\mu$ mol/L. It was concluded that more data is needed to optimize the performance of the tool for dark skin, including spectrophotometric measurements of skin color reflectance and newborns with higher bilirubin levels.

Currently, there is a running project in Uganda where data is collected from newborns with a broader range of bilirubin levels and high melanin content. Additional measurements of skin color reflectance with a spectrophotometer are made to adjust the Picterus JP algorithm and optimize the app performance. However, more data is needed to determine the adequacy of the app. Therefore, collecting data from different populations, such as in Botswana, will be valuable.

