#### 1.3. Purpose of study

This study will be conducted at a hospital in Botswana, where we aim to collect data from newborns with a broader range of bilirubin levels and high melanin content in a different population than in the Uganda study.

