#### **1.5. Specific Objectives**

The specific objectives of this study are:

- i. To assess the correlation between estimations of bilirubin obtained by Picterus JP with TSB, and TcB, in newborns with high melanin content in the skin.
- ii. To determine the accuracy of Picterus JP used as a screening tool to identify high levels of bilirubin in newborns with melanin content in the skin.

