#### 1.7. Justification

We hypothesize that the Picterus JP will offer bilirubin level estimates that are highly correlated to bilirubin levels measured in blood samples in a population in Botswana. Following our hypothesis, the short-term goal for this project is to demonstrate that this screening method can be used to identify children with severe neonatal jaundice independent of skin color. Thus, providing a cheaper, patient-friendly, and more readily available means of neonatal jaundice detection.

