#### 2.3. Study population and sample size calculations

The study population will comprise 150 newborns from the Neonatal Unit and the postnatal ward at Princess Marina Hospital, a number determined by a sample size calculation based on standard errors of the 95% limit agreement, as described by Bland and Alman.

The standard error of the 95% limit of agreement is given by  $\sqrt{\frac{3\times s^2}{n}}$ , where *s* is the standard deviation of the differences between measurements by the two methods, and *n* is the sample size.

The study performed at St. Olav Hospital showed a standard deviation (*s*) of the difference between bilirubin estimates from digital images to blood samples of 35  $\mu$ mol/L.  A sample size (*n*) of 150 participants will then give the confidence interval of the limits of 9,8  $\mu$ mol/L, a relevant size for clinical use.

The study objective of this study is two-folded. First, we wish to determine the correlation between TSB measurement and Picterus image estimate of serum-bilirubin. Second, we wish to determine the accuracy of the Picterus App used as a screening tool.

The study conducted by Aune et al. found an AUC of 0.925. To calculate the sample size for this study we used the used the EasyROC tool, by setting an AUC of 0.9, a significance level of 0.5 and a power to 0.8. This gave the suggested sample size of 12 infants. In order to get a sufficient result for all bilirubin levels, we decided to apply our pilot data to see how many subjects were needed to receive a sample of 12 in three different groups; <100  $\mu$ mol/L, 100-200  $\mu$ mol/L and >200  $\mu$ mol/L. Through this calculation we came to the number of 115 infants.

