#### 2.4. Participants and sampling procedure

Participants will be recruited from the NNU and postnatal ward at the Princess Marina Hospital. The parents of newborns with and without signs of jaundice will be asked to participate.

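### Section 2.3 presents the accuracy sample as adequate at every bilirubin level, but it contains no calculation for severe jaundice (TSB above 250 µmol/L), the condition the study aims to detect

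*Protocol*

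**What the plan says.** Section 2.3 contains two separate calculations. The first sets the study size: 150 infants, from the standard error of the limits of agreement with a standard deviation of 35 µmol/L. The second concerns the screening objective. An ROC tool with an AUC of 0.9 and power of 0.8 gave 12 infants. To make the result adequate at all bilirubin levels, the authors say "we decided to apply our pilot data to see how many subjects were needed to receive a sample of 12 in three different groups", namely below 100, 100-200 and above 200 µmol/L. That gave 115.

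Other sections set the target higher on the bilirubin scale:

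- Section 1.1 reports earlier performance for "severe jaundice, defined as TSB above 250" µmol/L.
- Section 1.2 reports the Uganda pilot at the same cut-off. Sensitivity was 66% in a study of 167 infants, and "Only six newborns had bilirubin levels higher than 250" µmol/L. It concludes that more data are needed, "including spectrophotometric measurements of skin color reflectance and newborns with higher bilirubin levels".
- Section 1.3 responds: "we aim to collect data from newborns with a broader range of bilirubin levels".
- Section 1.7 sets the short-term goal of demonstrating that "this screening method can be used to identify children with severe neonatal jaundice independent of skin color".
- Section 1.5, objective ii, is more general: the tool is to be "used as a screening tool to identify high levels of bilirubin in newborns with melanin content in the skin".

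On recruitment, section 2.4 says "The parents of newborns with and without signs of jaundice will be asked to participate". No section states an expected or minimum number of infants above 250.

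**The concern.** The stated goal is detection of severe jaundice, and the pilot's acknowledged weakness was that it had few severe cases. The sizing of the accuracy objective does not address that weakness. Two of its three bands contain no severe case by definition, and the third can be filled by infants between 200 and 250. The 12 placed in each band was derived for something else: a whole ROC sample of diseased and non-diseased infants together.

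Sensitivity for severe jaundice may therefore rest on a handful of infants, while section 2.3 tells the reader that every bilirubin level is covered. A high point estimate on a few cases could then be read as the demonstration that section 1.7 promises, when the interval around it would still allow about half of severe cases to be missed.

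**Working it through.** **Inputs.** From 2.3: N = 150, standard deviation 35, AUC 0.9, power 0.8, ROC total 12, and 115 infants for 12 per band. From 1.2: 6 of 167 above 250. From 1.1: severe jaundice is TSB above 250. Two assumptions are mine: that the pilot data in 2.3 are those of the Uganda pilot, the only one described, and the alternative rates in step 5.

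**1. The plan's 150.** The standard error is √(3 × 35² / 150) = 4.95. Multiplied by t(0.975, 149 df), this gives 9.78, which agrees with the stated 9.8. The calculation reproduces.

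**2. The plan's 12.** I used the Obuchowski binormal formula for one ROC curve, null AUC 0.5, alternative 0.9, power 0.8, equal groups. At a two-sided level of 0.05 it gives 6.25 cases plus 6.25 non-cases, about 12.5 in total. The Hanley-McNeil variance gives 6.1 plus 6.1. So 12 is a total of cases plus non-cases. It does not follow from the significance level of 0.5 as printed, which gives a total of 2 to 4; 0.05 is the reading that fits.

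**3. The plan's 115.** The pilot's band shares are not given, so this can only be solved backwards. If 115 infants give at least 12 in every band, each share is at least 12/115 = 10.4%. For 150 infants this implies at least 150 × 12/115 = 15.7, about 16, above 200 µmol/L. It says nothing about how many exceed 250.

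**4. Expected severe cases at the Uganda rate.** The rate is 6/167 = 3.6%.

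- Expected number in 115: 115 × 6/167 = 4.1.
- Expected number in 150: 150 × 6/167 = 5.4, with a binomial 95% range of 1 to 10.
- Probability of 7 or more in 150: 29%. Probability of 12 or more: 0.8%.
- The exact 95% CI of the pilot rate is 1.3% to 7.7%, which corresponds to 2.0 to 11.5 expected cases in 150.

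**5. What this gives for sensitivity at 250 (exact Clopper-Pearson 95% CI).** The local rate is not in the protocol, so a range is shown.

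| Rate above 250 | Expected cases in 150 | If all are detected | If one is missed |
|---|---|---|---|
| 3.6% (Uganda pilot) | 5.4 | 5/5: 48-100% | 4/5: 28-99% |
| 8% (assumed) | 12 | 12/12: 74-100% | 11/12: 62-99.8% |
| 10% (assumed) | 15 | 15/15: 78-100% | 14/15: 68-99.8% |

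**6. The AUC test itself.** At the pilot mix there are about 27 non-cases per case (161/6). The formulas in step 2 then need about 3.5 cases to show an AUC of 0.9 against 0.5, which is below the 5.4 expected. The weak quantity is sensitivity for severe jaundice, not the AUC test.

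**The case against.** The strongest reply has four parts.

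- **The study size does not come from the criticised step.** The 150 is set by the limits of agreement, and 115 is a secondary check that 150 exceeds. This stands: nothing here shows that 150 is wrong for the agreement analysis.
- **The cut-off of 250 is selective.** Objective ii speaks of high bilirubin in general, section 2.7.2 plans several cut-offs, and above 200 the plan's own figures imply about 16 infants, for whom 16/16 would give 79-100%. This stands in part: accuracy above 200 is better supported. But 250 is the protocol's only definition of severe jaundice and the cut-off of its pilot result, and severe jaundice is what section 1.7 names.
- **The Botswana rate is unknown.** The site is a referral hospital, and entry is limited to infants who need a blood sample for suspected jaundice or other screening. The pilot's entry rules are not described, so the mix here could be richer or poorer. This stands, which is why step 5 gives a range.
- **The pilot in 2.3 is not named.** This also stands. The 3.6% is a conditional figure, not a rate the protocol states.

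A reader might go further and infer that the study cannot improve on the pilot, or will have no more than six severe cases. The documents do not support either. No comparison with the pilot's 66% is planned, and that value fits 4 of 6, whose own exact 95% CI is 22-96%, so it is no firm benchmark. Even at the pilot rate there is a 29% chance of seven or more cases.

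**Conclusion.** The point holds in a limited form. Section 2.3 claims a property that its calculation does not deliver: a total for one ROC curve is reused as a count per band, and no band isolates the infants above 250 whom section 1.7 aims to identify. If the Uganda pilot rate applies, about 5 severe cases are expected and a perfect result would leave a lower confidence limit of 48%. At assumed rates of 8-10%, a perfect result would leave a lower limit of 74-78%. The first figure depends on the unnamed pilot being Uganda; the others depend on rates the protocol does not give.

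A reader might also conclude that 150 is too few and that recruitment should continue to a fixed number of severe cases. That does not follow. The 150 has its own valid basis, and at the pilot rate even 12 expected cases would need 12/(6/167) = 334 infants. What needs correcting is the claim, not the size of the study.

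**What to change.** Keep 150 infants.

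- **Section 2.3:** remove the statement that the sample is adequate at all bilirubin levels. In its place, give the expected number of infants above 250 µmol/L over a stated range of rates, with the exact 95% CI for sensitivity that each number allows, as in the table above. Name the pilot that supplied the band shares, and say that the 12 is a total of cases plus non-cases.
- **Section 1.7:** state that sensitivity at 250 is descriptive and will be reported with the number of cases and an exact 95% CI, and that it will not be presented as a demonstration that severe jaundice is identified.

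The cost is a few sentences and a more modest claim. Recruitment, procedures and budget do not change.

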#### 2.4. Participants and sampling procedure

Participants will be recruited from the NNU and postnatal ward at the Princess Marina Hospital. The parents of newborns with and without signs of jaundice will be asked to participate.

#### 2.5. Selection criteria

150 newborns will be included in this study. Participants will be recruited from the NNU and the postnatal ward.

#### 2.5.1. Inclusion criteria

- Gestational age  $\geq 37$  weeks
- Birth weight  $\geq 2000 \text{ g and } \leq 4500 \text{ g}$
- Age > 24 hours and < 14 days
- Infants requiring a blood sample for clinically suspected jaundice or other screening

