VA of neonatal jaundice is often based on the cephalocaudal progression of the yellowness using Kramer's scale, which assumes that a higher number corresponds to an increased level of serum bilirubin (Figure 1). This is the first-step screening option where other types of equipment are lacking.  Several studies have shown that VA is not a sufficient indicator on its own and unreliable as a screening tool for further testing. 

[figure not shown]

Fig. 1 Kramer's scale

To reduce the need to draw blood from the newborn, non-invasive devices that measure bilirubin concentration by shining light through the skin, such as transcutaneous bilirubinometers (TcB), have been developed.  TcB is one of the methods recommended by the American Academy of Pediatrics for the assessment of the risk of hyperbilirubinemia of newborns before discharge.  It is a safe, non-invasive method, and some studies have shown that its use can reduce the number of blood draws by 38,5%.  TcB shows a good correlation with blood samples, also in different ethnicities.  However, this is only true for the *BiliCheck* bilirubinometer. The *Minolta* bilirubinometer shows a higher transcutaneous bilirubin estimation in dark-skinned infants than in light-skinned infants. Additionally, it underestimates transcutaneous bilirubin when higher TSB levels are present. 

Lab equipment for TSB measurements and TcB devices is expensive, with a price range from 6.000 to 10.000 US dollars, thus making them practically unavailable in low-income countries. Because most deaths due to neonatal jaundice occur in low-income countries, there is a significant unmet need for simple, reliable, and affordable technologies to identify at-risk newborns. Mobile health, or mHealth, is an area with increased focus, as cell phone technology and smartphones are found worldwide, also in regions with scarce resources. This has given hope for new affordable solutions for global health. 

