#### 2.7.2. Statistical analysis

The bilirubin estimates from the images taken will be determined. The images will be compared to the TSB, NeoBil and TcB measurements using the Pearson correlation coefficient. Sub-analysis for the different skin colors, gestational ages, days of life, and bilirubin levels will be performed for the TSB and image estimate. Sensitivity and specificity analysis will be calculated for different cut-off values using the ROC analysis. Systematic over- or underestimation of bilirubin levels will be evaluated using Bland-Altman plots. To avoid bias, the developer of the product – Picterus AS – will not be involved in statistical work-up or even see the raw data.

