#### 2.8. Risk assessment

The overall assessment of risk in this study is considered low.

The procedure of obtaining the smartphone images involves no risk of importance. Blood samples will be obtained by the standard method, and no additional risk is involved in this study.

All bilirubin estimates from the digital images will be performed after collecting data, as the smartphone application has not yet been validated for this population. This leaves no risk of presenting false bilirubin estimates to participants.

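### Objective ii claims accuracy as a screening tool, but only infants already needing a blood sample can enter, and the single ROC analysis mixes two kinds of infant in an unfixed, unreported ratio.

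*Protocol*

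**What the plan says.** Protocol section 1.5 gives objective ii as "To determine the accuracy of Picterus JP used as a screening tool to identify high levels of bilirubin in newborns". Section 2.3 repeats the aim ("we wish to determine the accuracy of the Picterus App used as a screening tool"), and section 1.7 sets the short-term goal of demonstrating that "this screening method can be used to identify children with severe neonatal jaundice independent of skin color".

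Section 2.5.1 restricts entry to "Infants requiring a blood sample for clinically suspected jaundice or other screening". Section 2.4 adds that "The parents of newborns with and without signs of jaundice will be asked to participate", but gives no consecutive or random sampling and no quota. Section 2.8 states that "Blood samples will be obtained by the standard method, and no additional risk is involved in this study". Nothing suggests that infants without a need for blood are sampled for the study.

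Section 2.7.2 derives sensitivity and specificity at several cut-offs from a ROC analysis and states no stratification of it. It also says that "Sub-analysis for the different skin colors, gestational ages, days of life, and bilirubin levels will be performed" for TSB and the image estimate. Reason for the sample and ward are not among those subgroups. The background data listed in section 2.6 and in Appendix IV step 2 do not include the reason for the sample, although both lists are introduced as examples.

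**The concern.** Accuracy figures belong to the population in which they were measured. An infant who enters for suspected jaundice has already been flagged clinically. Section 1.1 says this is usually done by visual assessment in African countries, and adds: "Several studies have shown that VA is not a sufficient indicator on its own and unreliable as a screening tool for further testing". An infant who enters for another reason has not been flagged in that way. The two groups will probably differ in bilirubin level and in how many non-cases lie just under the threshold.

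If both go into one ROC analysis, the specificity, AUC and PPV partly reflect how many of each kind were recruited. A reader would take the result as the accuracy of a screening test, could not see the mix behind it, and could not carry it over to a setting with a different mix. If the reason for sampling is not captured at enrolment, there may be no reliable way to separate the groups afterwards.

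**Working it through.** **1. Aim against entry.** Sections 1.5, 1.7 and 2.3 speak of screening. Section 2.5.1 requires that a blood sample is already needed. Section 2.4 widens the range of infants approached but does not waive that condition. The population studied is therefore newborns selected for blood sampling.

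**2. The protocol's own figure, as a check on the SD used below.** Section 2.3 gives s = 35 µmol/L and n = 150. The standard error of a limit of agreement is √(3 × 35² / 150) = √24.5 = 4.95. The half-width is 1.96 × 4.95 = 9.70, or 1.976 × 4.95 = 9.78 with the t quantile, which matches the stated 9.8 µmol/L. That figure is sound and does not bear on this point; only the SD is carried forward.

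**3. Illustration of mix dependence.**

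- From the protocol: error SD 35 µmol/L (2.3), and TSB above 250 µmol/L as the target, the threshold used for the earlier results in 1.1 and 1.2. Section 2.7.2 itself leaves the cut-offs open.
- Assumed: TSB about N(220, 60) in suspected-jaundice infants and N(120, 60) in the others; the app estimate equals TSB plus an unbiased normal error, the same in both groups.

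Simulated results by group at app cut-off 250:

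| Group | Share of cases | Sensitivity | Specificity | AUC |
|---|---|---|---|---|
| Suspected jaundice | 0.308 | 0.794 | 0.872 | 0.92 |
| Other reason | 0.016 | 0.70 | 0.979 | 0.98 |

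With suspected share w, p the share of cases and Sp the specificity (subscript S for suspected, O for other):

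pooled specificity = [w(1 − p_S)Sp_S + (1 − w)(1 − p_O)Sp_O] / [w(1 − p_S) + (1 − w)(1 − p_O)]

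- w = 0.20: (0.1384 × 0.872 + 0.7872 × 0.979) / 0.9256 = 0.8914 / 0.9256 = 0.96
- w = 0.80: (0.5536 × 0.872 + 0.1968 × 0.979) / 0.7504 = 0.6754 / 0.7504 = 0.90

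Pooled sensitivity weights by cases instead:

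- w = 0.20: (0.0616 × 0.794 + 0.0128 × 0.70) / 0.0744 = 0.78
- w = 0.80: (0.2464 × 0.794 + 0.0032 × 0.70) / 0.2496 = 0.79

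In the same simulation the AUC moves from 0.97 to 0.94 and the PPV from 0.62 to 0.72. The device error is identical throughout; only the mix changes.

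**4. Lower app cut-off, same target.** At app cut-off 200 the simulated specificities are 0.550 (suspected) and 0.884 (other).

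- w = 0.20: (0.1384 × 0.550 + 0.7872 × 0.884) / 0.9256 = 0.83
- w = 0.80: (0.5536 × 0.550 + 0.1968 × 0.884) / 0.7504 = 0.64

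Sensitivity is about 0.98 at both mixes.

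**5. Other assumed distributions.** With non-cases about N(180, 50) and N(100, 40), truncated at 250, specificity at app cut-off 200 is 0.68 and 0.97. Mixing non-cases 20:80 gives 0.20 × 0.68 + 0.80 × 0.97 = 0.91, and 80:20 gives 0.80 × 0.68 + 0.20 × 0.97 = 0.74. At app cut-off 250 the group values are 0.93 and nearly 1.00, so the mix matters much less.

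**6. Cases available.** The Uganda pilot had 6 of 167 infants above 250 µmol/L (section 1.2), or 3.6%. At that rate 150 infants give 150 × 6/167 = 5.4 cases in all. If 75 infants entered for another reason, the assumed 1.6% gives 75 × 0.016 = 1.2 cases. Sensitivity and AUC within a stratum would then carry almost no information. Specificity, which rests on non-cases, can be estimated in both.

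**The case against.** **The design is ethical and deliberately broad.** Taking blood only where it is already needed avoids study-only sampling, and sections 1.3 and 2.4 seek a wide bilirubin range from two wards. This stands, and the entry rule need not change. It does not make the pooled figure a screening accuracy.

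**Screening can mean deciding who needs a TSB.** Appendix V describes a comparable app in that way, and the protocol nowhere says that the app replaces visual assessment. That is fair. Even so, deciding whether a TSB is needed comes before the selection made here, because every participant already needs a blood sample.

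**The SAP may stratify, and the CRF may hold the reason.** Neither is at hand, and the data lists are illustrative. A reader might infer that the groups can never be separated; the document shows only that capture of the reason is not assured. Pooling is likewise inferred from section 2.7.2, which does not use the word. Capture must nevertheless be secured at enrolment, which a later SAP cannot do, and the wording of the aim is protocol content.

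**The effect rests on assumed distributions.** This stands. A reader might take the gap of 68% to 97% in specificity as the possible range of the pooled result. It needs all-or-none recruitment at app cut-off 200, which section 2.4 does not envisage. The illustration also gives no support for saying that sensitivity depends materially on the mix.

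**Conclusion.** The point holds as a mismatch between the stated aim and the population that can enter, made worse by one unstratified ROC analysis. Pooled specificity, AUC and PPV depend on a mix that is neither fixed nor planned to be reported. Under the assumed distributions, a suspected share between 20% and 80% moves specificity at cut-off 250 by about 0.06 (0.96 to 0.90), with sensitivity at 0.78 to 0.79. At app cut-off 200 the same change moves specificity by about 0.2. Only the SD of 35 µmol/L and the 250 threshold come from the protocol, so neither the size nor the direction of any departure from true screening accuracy can be derived from it.

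Two stronger readings are not supported. One is that infants missed by eye enter only by accident: the other-screening route admits them expressly, and if it means routine sampling of unselected newborns, that stratum could come close to a screening population. The protocol does not define it. The other is that only the infants sampled for other reasons bear on first-line screening: an unselected newborn population also contains visibly jaundiced infants, so neither stratum alone represents it.

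**What to change.** 1. Add the reason for the blood sample (suspected jaundice / other) to the CRF and to Appendix IV step 2.
2. In section 2.7.2, report the numbers of infants and cases and the specificity by that reason beside the pooled figure. Give sensitivity and AUC by stratum only descriptively, because cases will be few.
3. Word objective ii and section 1.7 as accuracy in newborns already having blood sampled, without presenting either stratum as an unselected screening population.

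The cost is one tick-box, one table and a change of wording. No extra infants, blood or visits are needed. The price is small strata with wide intervals and a narrower screening claim.
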